## 2. Purpose of the study

- a) **Provide a brief lay summary of the project in <200 words. The lay summary should be readily understandable to the general public.**

Surgery on the frontal sinus is done for patients who have sinus problems that do not respond to medications. It involves making an opening within the right and left frontal sinus of the nose to help it drain. For severe frontal sinus disease the sinus is widely opened and the left and right sinuses become one large sinus. This is done with sharp instruments and rigid endoscopes placed through the nostrils. While the sinus heals after surgery, a stent or steroids or both may be used to try to help make sure that the opening does not close back up. Two current options for this are Propel stents and steroid-soaked Nasopore. Propel stents are FDA-approved. Nasopore and kenalog injection are both FDA-approved, but their use together is part of the study and not specifically FDA-approved. A previous study shows that Propel stents are useful to reduce scarring in other frontal sinus procedures. We would like to know whether this is true in larger frontal sinus surgery where one common cavity is made and whether both steroid-containing stents are the same.

Page numbers from a sponsor's protocol/grant may be referenced in 2b and 2c.

- b) **List your research objectives (specific aims & hypotheses of the study).**

Aim 1: To compare the difference in mean post-operative SNOT-22 scores between the Propel stent and Nasopore groups.

Aim 2: To compare the incidence of other surgical postoperative complications (diagnosed post-operative CSF leak, epistaxis requiring treatment, adhesions) between Propel stent and Nasopore.

Aim 3: To ascertain the incidence of surgical complications based on the specific frontal sinus

**Protocol Title:** Randomized trial of Propel stent vs Kenalog-soaked Nasopore after Frontal Drill-out

---

pathology

Hypothesis: Patients in the Kenalog-soaked Nasopore group will have outcomes that are non-inferior compared to the Propel stent group when comparing the long term symptom control as measured by SNOT-22 scores at 24 months follow-up.

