Note that to maintain uniformity in care, post-operative antibiotics (defined as up to day 60 post-op) will only be given to patients in any group if frank purulence is noted intra-operatively. In addition, in accordance with other trials involving drug eluting stents [1], oral and topic steroids will not be given to patients in any group until 60 days post-operatively. Because oral steroids and certain antibiotics have anti-inflammatory properties, this could confound the result of the study. For this reason, we wish to avoid using them in a random fashion.

- c) **If the proposed study is a clinical trial where a drug, vaccine, device or other treatment is compared to a placebo group or comparison treatment group, what are the guidelines or endpoints by which early decisions regarding efficacy or lack of efficacy can be made? For example, it may be reasonable to stop enrollment on a study when efficacy has already been clearly demonstrated, to avoid unnecessary enrollments of additional subjects. Alternatively, it may be reasonable to stop enrollment when it is clear that efficacy will never be demonstrated, given the statistical power of the study as designed. Describe the guidelines that are in place to assist in making these determinations, if relevant to the proposed study.**

A difference in mean post-operative SNOT-22 score of 9 points will be considered a clinically significant difference. [1]

As such, preliminary analyses will be performed once 5 patients have been enrolled and then every 6 months thereafter until 2 years of follow up of the last subject. If clear statistically significant inferiority or superiority is demonstrated, the trial will be stopped.

[1] Chowdhury NI, Mace JC, Bodner TE, et al. Investigating the minimal clinically important

**Protocol Title:** Randomized trial of Propel stent vs Kenalog-soaked Nasopore after Frontal Drill-out

difference for SNOT-22 symptom domains in surgically managed chronic rhinosinusitis. Int Forum Allergy Rhinol. 2017;7(12):1149-1155.

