- d) **Describe how data analysis will be performed (statistical tests, methods of evaluating data) and indicate the smallest group/unit for which separate reporting will occur. For studies involving a questionnaire, if data and reliability information are available, please describe or provide references. For full board, unfunded studies describe sample size determination and power analysis. If none, please justify.**

The SNOT-22 score assesses symptomatic improvement and burden for patients with rhinosinusitis and is a clinically validated measure with high internal validity, correlation to its impact on quality of life, and longitudinal stability after sinus surgery. The minimal clinically important difference (MCID) for SNOT-22 is 9 points. [1, 2, 3, 4,5] From historical SLU otolaryngology practice data, patients who present to the otolaryngology clinic undergoing sinonasal surgery have a mean SNOT-22 score of  $42.0 \pm 8.0$ .

For this randomized, active control study of two types of sinonasal stents with steroid, we are interested in determining whether the cheaper and more available alternative (Nasopore and Kenalog) is similar to an accepted treatment (Propel stent) in symptom control at 24 months as measured by post-operative SNOT-22 scores.

For our sample size determination, we explore the lower limit of a 95% confidence interval (CI) around the mean difference between post-operative SNOT-22 scores of the two groups. We'll define the lower limit of the CI, or the margin of inferiority, as -8, which does not include the predetermined MCID of -9.  
We set power = 0.8 and alpha = 0.05.

Given: # subjects in each group =  $n = [(2(SD)^2) * (z_{1-(\alpha/2)} + z_{1-B})^2] / [(u_1 - u_2)^2]$  [ref 6]  
SD = 8.0, from SLU historical data  
 $[(z_{1-(\alpha/2)} + z_{1-B})]^2 = 7.8$ , estimated from z-tables,  $\alpha = 0.05$  and  $B = 0.2$

IF  $u_1 - u_2 = -8$  then  $n = 16$  subjects

To be conservative in our sample size calculation, we'll use  $u_1 - u_2 = -5$ , which yields a sample size of 40.

If we assume attrition rate of 10%, we estimate we'll need 45 subjects per group and a total of 90 subjects.

Difference in rates of complications will also be determined by chi-square testing for equality of proportions between groups. As these outcomes are expected to be few, our target sample size may not be adequate to determine statistical significance of differences. Reporting these complication rates nonetheless informs clinical practice.

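### Section 3c makes stopping mandatory at about eight interim looks, but sets no interim significance boundary, SNOT-22 visit or inferiority reference; at the plan's only alpha, false superiority rises from 2.5% to about 6-8%

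*Combined protocol and SAP*

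**What the plan says.** Section 3c (early decisions on efficacy) opens with a clinical benchmark: "A difference in mean post-operative SNOT-22 score of 9 points will be considered a clinically significant difference". It then sets the schedule ("preliminary analyses will be performed once 5 patients have been enrolled and then every 6 months thereafter until 2 years of follow up", which for this purpose means follow-up of the final patient enrolled) and the consequence: "If clear statistically significant inferiority or superiority is demonstrated, the trial will be stopped". Sections 2c and 8k repeat the schedule without adding a rule.

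The quantities one would need to apply the rule appear elsewhere, attached to other purposes:

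- Section 3d, under sample size: "We set power = 0.8 and alpha = 0.05", and the intention to "define the lower limit of the CI, or the margin of inferiority, as -8". The planning difference of -5 is the one "which yields a sample size of 40" per group.
- Section 2b, in the hypothesis: "long term symptom control as measured by SNOT-22 scores at 24 months follow-up". Section 3d also refers to 24 months.
- Sections 2c and 3b collect SNOT-22 at five post-operative visits: weeks 1-2, weeks 6-8, and months 6, 12 and 24.

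No sentence applies the alpha, the margin or the 24-month visit to the interim looks. The data safety monitoring plan (section 9, item 11b) answers n/a on stopping rules and gives a further trigger for aggregate review, every 10 patients completing follow-up.

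**The concern.** The stop is mandatory, so two people holding the same data should reach the same decision. Under 3c they need not. Five things are left open: the p-value or boundary, the meaning of *clear*, the visit compared, the value against which inferiority is judged, and whether the 9-point difference must also be reached.

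The default reading is also a problem. The only alpha in the documents is a fixed-sample 0.05. Used again at each look, it no longer gives a 5% error rate. At stake are any superiority or inferiority claim made on stopping and the reproducibility of the stop itself.

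The visit matters because of timing. Recruitment takes 2 years and the hypothesis is at 24 months, so looks made during recruitment hold essentially no 24-month scores. A stop at that stage would have to rest on scores from visits that do not test the stated hypothesis.

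**Working it through.** **Inputs from the documents.** SD 8.0, two-sided alpha 0.05, power 0.80, margin -8, planning difference -5, 10% attrition, 90 subjects (3d); 1:1 allocation (2c); 2-year recruitment and up to 4 years in total (8k).

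**Assumptions.** Even accrual; surgery 0-2 months after enrolment (section 13 places consent at an outpatient visit before the procedure); t-tests; final test at 0.05. Differences are signed so that negative means Nasopore is worse; 3d does not define its two means, so this is a convention. A trial stopped for superiority is counted as having shown non-inferiority.

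**1. The plan's own figures.** n = 2 × SD² × 7.8 / difference².
- Difference 8: 2 × 64 × 7.8 / 64 = 15.6, so 16.
- Difference 5: 2 × 64 × 7.8 / 25 = 39.9, so 40.
- Attrition: 40 / 0.9 = 44.4, so 45 per group and 90 in total.

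These reproduce. With no looks and equal packings, non-inferiority power is Φ(8 / (8 × √(2/40)) - 1.96) = Φ(4.47 - 1.96) = 0.994.

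**2. Number of looks.** Accrual is 90 / 24 = 3.75 per month, so 5 are enrolled at month 5 / 3.75 = 1.33. Six-monthly looks follow at 7.33, 13.33, 19.33, 25.33, 31.33, 37.33 and 43.33. That is eight interim looks, with the final analysis at month 48. A 2-month surgery delay gives nine.

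**3. 24-month scores available** (no delay, mean after 10% attrition): 0, 0, 0, 0, 4.5, 24, 45 and 65 at the eight looks, and 81 at the end. The first four looks are empty. The first with any data falls at month 25.3, after planned enrolment ends.

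**4. What the reference changes.** At the month-37 look, with 50 scores before attrition, the standard error is 8 × √(4/50) = 2.26. Two-sided p<0.05 then needs an observed difference of about 4.6 against 0, or 8 + 4.6 = 12.6 against -8.

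**5. Error rates with p<0.05 at every look** (simulation, 24-month scores, packings equal, at least 20,000 trials per setting; ranges cover surgery delay and whether the look with 4-5 completers is tested):

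| | No looks | Inferiority against 0 | Inferiority against -8 |
|---|---|---|---|
| False superiority | 2.5% | 6-8% | 6-8% |
| False inferiority | 2.5% | 6-8% | under 1% |
| Any false finding (test against 0) | 5% | 12-16% | - |
| Non-inferiority shown | 99% | 92-95% | about 99% |

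As a cross-check, five equally spaced analyses at 0.05 give 14.1%.

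**6. The non-inferiority claim.** At a true difference of -8, non-inferiority is wrongly shown in about 2.4% of trials with no looks, about 1% with looks against 0, and about 2.8% with looks against -8.

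**7. A strict boundary.** With p<0.001 at interim looks and 0.05 at the end, two-sided error is about 5% and non-inferiority is shown in about 99%.

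**The case against.** The strongest reply is that the documents can be read together. The only number attached to inferiority is -8, in the section that follows 3c, and both the hypothesis and 3d point to 24 months. On that reading false inferiority is under 1%, non-inferiority power is untouched, and only false superiority of 6-8% remains, for a claim that is not the hypothesis. *Clear* may also be meant to be stricter than 0.05. Much of this stands: it is a reasonable reading, and it limits the harm. But 3c does not adopt it, and even this reading leaves the boundary unstated and false superiority above 2.5%.

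Four stronger readings are tempting and are not supported.

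- A reader might infer that the primary non-inferiority conclusion is compromised. Step 6 shows that it is not.
- A reader might suppose that looks during recruitment would use each patient's latest score, which would inflate error further. No such rule is in the documents, and its size depends on a between-visit correlation they do not give.
- At a true 5-point disadvantage, the chance of an early inferiority stop on 24-month scores runs from about 1% (p<0.05 against -8) to about 75% (p<0.05 against 0). A reader might take the 75% as error. It is mostly planned power: a trial with no looks reaches p<0.05 against 0 in about 79%. The spread does show how much the undefined terms matter.
- A reader might count eight tests of the endpoint. On 24-month scores only four interim looks hold data.

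Saving enrolment ("to avoid unnecessary enrollments of additional subjects") is an example in the form's prompt, not an aim stated by the sponsor, so a 24-month rule does not fail the plan on that ground. The n/a in the safety monitoring plan answers a safety question and need not contradict an efficacy rule.

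**Conclusion.** The point holds and should be corrected before the rule is used. Section 3c orders a stop without an interim boundary, a visit or an inferiority reference, and applying the only alpha in the plan at each look gives wrong error rates: about 6-8% false superiority instead of 2.5% on either reference and, if inferiority is judged against 0, about 12-16% false findings instead of 5% with a loss of roughly 4-7 percentage points in non-inferiority power. That power stays well above the planned 80%.

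The harm is to superiority and inferiority claims and to the reproducibility of a mandatory stop; the primary non-inferiority claim is not put at risk.

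The figures rest on SD 8, 10% attrition, even accrual, 24-month scores and p<0.05 at each look. The number of looks shifts with accrual and surgical delay; the missing specifications do not depend on either.

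**What to change.** Amend section 3c as follows.

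1. Replace *clear* with a pre-specified strict interim boundary, for example two-sided p<0.001 at each interim look or an alpha-spending boundary, and keep the 95% confidence interval at the final analysis.
2. Name the SNOT-22 visit compared. It should be 24 months if the stop is to test the stated hypothesis. With even accrual the first four looks then hold no data for the rule and can serve safety review only; say so.
3. State whether inferiority is judged against 0 or -8, and whether the 9-point difference must also be met.
4. Minor: cross-refer items c to e of the data safety monitoring plan (section 9, item 11b) to 3c, so that the review triggers and the n/a on stopping rules are read consistently.

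This is protocol wording only and needs no extra patients. The cost is fewer early stops. On 24-month scores against 0, a true 5-point difference would stop early for inferiority in about 21% of trials at p<0.001 instead of about 75% at p<0.05; for a 9-point difference, about 85-86% instead of 99%. A 24-month rule also cannot stop enrolment early. If the sponsor values such a stop, 3c could name one earlier visit with the same boundary and acknowledge that it does not test the 24-month hypothesis. That is a trade-off for the sponsor to decide, not a required change.

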**Please save frequently**

- c) **Describe the study design (e.g., single/double blind, parallel, crossover, control, experimental, observational, etc.). If the study is investigator-initiated, a timeline for individual subject recruitment, follow-up, and analysis for the study is required. Also, indicate if the subjects will be randomized.**

Single blind (Subject) randomized, active control study. Subjects will be randomized 1:1 using the rand function in Microsoft Excel program.

Timeline: There will be a 2 year recruitment period during which patients will be recruited and eligible to participate. Eligible patients are those with chronic inflammatory sinonasal disease for whom frontal drill out procedure is indicated after evaluation by otolaryngologist. Patients eligible for the study and consenting to participate will be randomly assigned to one of two treatment groups: 1) Nasopore group will receive frontal drill out procedure as indicated with Kenalog-soaked Nasopore stent applied to the post-operative outflow tract and 2) Propel stent group will receive frontal drill out procedure as indicated followed by Propel stent placement applied to the post-operative outflow tract.

After the surgery, we will ask patients to follow up 5 times: post-operatively once between week 1-2, once between week 6-8, month 6, month 12, and month 24. All visits are standard of care.

During those visits, patients will fill out a short research related questionnaire that will ask about whether or not their symptoms have improved after surgery. We will also assess sinus cavities with rigid nasal endoscopy. Surgical complications will be documented and SNOT-22 scores will be determined by patients filling out SNOT-22 questionnaire at each visit.

Preliminary analysis will be performed once 5 patients have been enrolled and then every 6 months thereafter until 2 years of follow up of the last subject. We expect enrollment to occur over a period of 2 years.

- d) **If subjects will be given placebo, please justify placebo use. \*?HELP?\***

N/A

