**j) Describe who will cover study related costs. Explain any costs that will be charged to the subject.**

All procedures are standard of care; no additional research related costs will be incurred. Insurance will be billed for the standard of care procedure. Any administrative costs will be covered by the Otolaryngology department.

**k) Estimate the probable duration of the entire study including data analysis and publication. This estimate should include the total time each subject is to be involved and the duration the data about the subject is to be collected. If the study is Investigator-initiated, a timeline for individual subject recruitment, follow-up, total time for subject accrual, and data analysis for the study is required.**

The total length of study can be up to 4 years from enrollment to completion. Recruitment will take place over a two year time period. The total timeline of subject involvement will be 2 years (follow-up visit

**Protocol Title:** Randomized trial of Propel stent vs Kenalog-soaked Nasopore after Frontal Drill-out

---

schedule previously described). Preliminary analysis will occur once 5 patients have been enrolled and then every 6 months thereafter. Data analysis and publication of data after all follow-ups are completed will take approximately one year after completion of follow-up. Each subject, after consenting and undergoing the procedure, will be then followed for two years, which is when post-operative data will be collected. Pre-operative data will be obtained at the time of consent.

---

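### Section 3c does not limit an early stop to enrolment; if follow-up ended too, a stop at six of about eight looks would leave most or all randomised patients without the 24-month SNOT-22 score

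*Combined protocol and SAP*

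**What the plan says.** - **Stopping rule (Section 3c).** "If clear statistically significant inferiority or superiority is demonstrated, the trial will be stopped". Nothing is said about patients already randomised.
- **The prompt that 3c answers.** It is framed around enrolment: "it may be reasonable to stop enrollment on a study when efficacy has already been clearly demonstrated, to avoid unnecessary enrollments of additional subjects". The answer does not use that word.
- **Looks (Section 3c).** "preliminary analyses will be performed once 5 patients have been enrolled and then every 6 months thereafter until 2 years of follow up of the" (the sentence closes by naming the final patient enrolled).
- **Timeline.** Section 2c: "There will be a 2 year recruitment period during which patients will be recruited and eligible to participate". Section 8k: "The total timeline of subject involvement will be 2 years" and "The total length of study can be up to 4 years from enrollment to completion".
- **Endpoint (Section 2b, hypothesis).** Non-inferiority is claimed for "long term symptom control as measured by SNOT-22 scores at 24 months follow-up". Section 3d names the same time point.
- **Treatment (Sections 2c and 3b).** The stent or soaked packing is placed once, at the frontal drill-out.
- **Follow-up (Sections 2c, 3b and 3f).** Visits, endoscopy and SNOT-22 through month 24 are standard of care, and the study abstracts the data from the record.
- **Monitoring plan (Section 9, item 11).** No data monitoring committee is described. The principal investigator monitors the data, adverse events are reviewed on the same six-monthly schedule, and item e), on stopping or halting rules, is answered n/a.

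**The concern.** Because treatment is a single act at surgery, an early stop can protect only people who have not yet been operated on. Ending follow-up of those already treated protects nobody and removes the scores that the hypothesis needs. The rule does not separate these two actions, and half of its looks fall when only the second remains possible.

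A stop during accrual would have to rest on scores from earlier post-operative visits, because no patient can yet have a month-24 score. If follow-up then ended, the 24-month hypothesis would never be tested. A stop in the year after accrual would leave a comparison based on the earliest-enrolled patients only.

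The question would also have to be settled mid-trial, by an investigator who has seen the interim result: only subjects are blinded and there is no independent committee. A well-specified interim boundary would not resolve this, since the issue is what happens to randomised patients after the boundary is crossed.

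**Working it through.** **The plan's own figures first (Section 3d).** n per group = 2·SD²·7.8/d², with SD = 8.
- d = 8: 2·64·7.8/64 = 15.6, so 16.
- d = 5: 2·64·7.8/25 = 39.9, so 40.
- 10% attrition: 40/0.9 = 44.4, so 45 per group and 90 in total.

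These reproduce. The sample size is not affected by this point.

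**Inputs.** N = 90, SD = 8, margin 8 and attrition 10% (Section 3d); accrual 24 months (Section 2c); follow-up 24 months and total length 48 months (Section 8k); first look at 5 enrolled, then every 6 months (Section 3c). The documents do not give the accrual pattern. Even accrual is assumed as the base case, with a slow-start and a fast-start curve as the range.

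**Method.** Let F(t) be the fraction randomised by month t.
- Randomised at a look = 90·F(t); at month 24 = 90·F(t − 24).
- Even accrual: 90/24 = 3.75 per month, so the first look is at 5/3.75 = 1.33 months.
- Slow start: F = (t/24)². First look at 5.66 months.
- Fast start: F = 1 − (1 − t/24)². First look at 0.68 months.

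All three give eight looks by month 48. Fractions below are expected counts.

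| Look | Month (even) | Randomised | At month 24 | Share (even) | Share over the three curves | Not yet at month 24 (even) | Still to randomise |
|---|---|---|---|---|---|---|---|
| 1 | 1.3 | 5 | 0 | 0% | 0% | 5 | 85 |
| 2 | 7.3 | 27.5 | 0 | 0% | 0% | 27.5 | 62.5 |
| 3 | 13.3 | 50 | 0 | 0% | 0% | 50 | 40 |
| 4 | 19.3 | 72.5 | 0 | 0% | 0% | 72.5 | 17.5 |
| 5 | 25.3 | 90 | 5 | 6% | 6% | 85 | 0 |
| 6 | 31.3 | 90 | 27.5 | 31% | 24–48% | 62.5 | 0 |
| 7 | 37.3 | 90 | 50 | 56% | 54–78% | 40 | 0 |
| 8 | 43.3 | 90 | 72.5 | 81% | 81–97% | 17.5 | 0 |

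Under every curve, looks 1 to 4 have no 24-month data and looks 5 to 8 come after accrual closes. With 10% attrition and even accrual, observed 24-month scores cover about 5%, 27%, 50% and 72% of the 90 at looks 5 to 8.

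**Precision if follow-up ended at look 6.** Half-width of the 95% interval = 1.96·8·√(2/n), with n per arm.
- Planned, 40 per arm (attrition already taken off): 15.68·√(2/40) = 3.5.
- Look 6, even accrual, 10% attrition: n = 0.9·27.5/2 = 12.4, giving 15.68·√(2/12.4) = 6.3. Without attrition n = 13.75, giving 6.0.
- Slow start, 21.2 patients at month 24: n = 0.9·21.2/2 = 9.5, giving 7.2.
- Fast start, 43.1 patients: n = 0.9·43.1/2 = 19.4, giving 5.0.

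**The case against.** The strongest reply is that 3c answers a prompt about stopping enrolment and never says that follow-up ends. Section 8k says without exception that each operated subject is followed for two years, and the clinic would generate the 24-month scores anyway as standard of care. On that view one clarifying sentence is enough.

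Part of this stands. The end of follow-up is the natural reading of stopping the trial, but it is not stated, so the losses above are conditional on it. The reply does not remove the problem, for two reasons. First, the rule remains in force for about 2 years after recruitment closes, and a rule about enrolment would then have nothing to act on. Second, Section 8k describes the ordinary course and does not address a stop; scores in the clinical record help the trial only if the study goes on abstracting them.

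Three stronger readings are tempting, and the documents do not support them:
- *Any stop leaves most or all patients without the endpoint.* At looks 7 and 8 a majority have reached month 24 under every curve tried, although with 10% attrition and even accrual look 7 is only about 50%.
- *A late stop does nothing but discard data.* It would also bring earlier reporting. In addition, a patient randomised just before closure may still await surgery at look 5, so it is not certain that all 90 have been treated by then.
- *The n/a in the monitoring plan contradicts 3c.* That item sits in a safety monitoring plan and may mean only that there is no safety halting rule. It is an inconsistency to reconcile, not a proven contradiction.

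**Conclusion.** The point holds in conditional form. Section 3c does not limit a stop to enrolment and keeps the rule active when follow-up is all that is left to stop. Independently of how that is read, no stop during accrual can rest on the 24-month hypothesis. If follow-up ends at a stop, the first six of about eight looks leave most or all randomised patients without the 24-month score, and the last two still lose about 40 and 17 patients. At look 6 the interval would be about 1.8 times as wide as planned (6.3/3.5), with a half-width not far below the margin of 8.

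The counts rest on 90 patients enrolled over exactly 24 months, evenly in the base case; the precision figures also rest on the plan's SD of 8 and 10% attrition. Slower or faster early accrual moves look 6 between 24% and 48% complete but does not change the pattern. The plan should be amended on this point; it does not invalidate the design.

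**What to change.** Reword Section 3c along these lines:

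*If the stopping criterion is met, enrolment stops. All patients already randomised continue SNOT-22, endoscopy and complication data collection to month 24, and the 24-month comparison is reported on all of them.*

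This agrees with the two-year follow-up in Section 8k. State also that once the last patient has been operated on, the remaining looks are safety reviews and carry no efficacy stop. In Section 9, item 11, replace the n/a at item e) with a cross-reference to 3c, or say that it refers to safety halting only.

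The cost is a wording amendment and continued record abstraction; the visits and questionnaires are already standard of care to month 24. Safety oversight is not reduced, because the six-monthly adverse event review in item d) stands on its own. The real downside is that a result that would have triggered a late stop is reported later.

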**Please save frequently**

- e) **State if deception (including incomplete disclosure of study purpose/procedures) will be used. If so, describe the nature of the deception and provide a rationale for its use. Also, describe debriefing procedures or justify a waiver of the requirement to debrief. NOTE: for studies using deception, an alteration of consent must be justified in the Informed Consent section of the protocol (#13) and the debriefing script/statement must be uploaded in the Attachments section (#16). See IRB Deception Guidelines.**
- f) **Is there an accepted standard of care and/or standard practice at SLU for the condition/disease/situation being studied? This information will assist in comparing the risk/benefit ratio of study procedures relevant to usual care that would be received outside of the research context. \*?HELP?\*** Y

**If yes, please describe the standard of care and standard practice at SLU for the condition/disease/situation being studied.**

Pre-operative CT scan is standard of care for patients with chronic inflammatory frontal sinus pathology who are going to undergo surgery.  
There is no specific standard of care for follow-up of chronic inflammatory sinonasal pathology and is left up to the discretion of the attending otolaryngologist. The standard of care for follow-up of chronic inflammatory sinonasal disease in SLU rhinology practice is what is proposed in this study (post-op week 1-2, week 6-8, month 6, month 12, month 24, and yearly thereafter). SNOT-22 questionnaire is standard of care for every patient at every visit in SLU rhinology practice.  
The standard of care for use of Propel stent and nasopore placement as well as topical nasal steroid at the discretion of the attending surgeon and based on patient's disease process, and these or a combination of these are routinely used in a large number of patients in a variety of procedures currently.  
Rigid nasal endoscopy is standard of care at all follow-up visits for all patients with chronic inflammatory sinonasal disease.  
As standard of care, patients may receive post-operative oral steroids or antibiotics based on intra-operative findings or the discretion of the attending surgeon. Strong evidence for or against use of antibiotics or oral steroids after sinus surgery is not found in the literature and it is considered an option based on current guidelines.[1]  
The only non-standard of care portion of the protocol is placement of Kenalog within Nasopore.

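### Section 3d plans the 24-month SNOT-22 comparison on an SD from patients presenting for sinus surgery in general, and leaves unused the preoperative score that would protect its precision

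*Combined protocol and SAP*

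**What the plan says.** **Source of the SD.** Section 3d states: "From historical SLU otolaryngology practice data, patients who present to the otolaryngology clinic undergoing sinonasal surgery have a mean SNOT-22 score of" 42.0 ± 8.0. The sample-size inputs then list "SD = 8.0, from SLU historical data". No other SD appears in the plan.

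**Outcome being sized.** The hypothesis in section 2b is non-inferiority of Kenalog-soaked Nasopore "when comparing the long term symptom control as measured by SNOT-22 scores at 24 months follow-up".

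**Margin and planning value.** Section 3d says: "We'll define the lower limit of the CI, or the margin of inferiority, as -8, which does not include the predetermined MCID of -9". It first enters -8 in the formula and obtains 16 per group. It continues: "To be conservative in our sample size calculation, we'll use" a difference of -5, which gives 40 per group, then 45 after 10% attrition and 90 in total. It does not say what the step from -8 to -5 is meant to cover.

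**Analysis.** The only description for the main outcome is a 95% CI around the difference between the two groups' post-operative means. No covariate is named. Section 3b provides for a preoperative SNOT-22 as part of standard care.

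**Routine data.** Section 3f says "SNOT-22 questionnaire is standard of care for every patient at every visit in SLU rhinology practice" and gives the practice's follow-up schedule as "post-op week 1-2, week 6-8, month 6, month 12, month 24, and yearly thereafter".

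**The concern.** The SD does not match the outcome in two respects. It appears to describe scores at presentation, whereas the comparison is at 24 months after surgery. It also covers sinus surgery broadly, whereas the trial enrols candidates for drill-out, which section 1 describes as the more extensive operation used in recalcitrant cases. Section 3d offers no argument that the spread carries over, and no sensitivity range in case it does not.

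If the 24-month SD is larger, the confidence interval widens. A Nasopore result truly inside the margin could then fail to show non-inferiority, and the cheaper option would go unsupported for lack of precision. The trial's own 24-month scores would reveal this late. Section 2c says "There will be a 2 year recruitment period during which patients will be recruited and eligible to participate", so those scores begin to arrive only as recruitment closes. That makes it worth choosing, before the data are seen, an analysis that gets the most precision from the patients already planned.

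**Working it through.** **Inputs from section 3d.** SD 8.0; margin 8 in absolute value; planning difference 5; alpha 0.05 two-sided; power 0.8; squared z-sum 7.8; attrition 10%. SDs other than 8, all true differences and all correlations below are assumptions, because the documents give none. A true disadvantage means that the Nasopore mean is worse by that many points, with a higher score taken as worse.

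**Step 1: the plan's own figures.** n per group = 2 × SD² × 7.8 / d².
- d = 8: 2 × 64 × 7.8 / 64 = 15.6, so 16.
- d = 5: 2 × 64 × 7.8 / 25 = 39.9, so 40.
- Attrition: 40 / 0.9 = 44.4, so 45 per group and 90 in total.

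All three reproduce.

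**Step 2: power of 40 evaluable per group against margin 8.** Power = Φ[(8 − true) / (SD × √(2/40)) − 1.96], the normal approximation that the plan's formula uses. Example, SD 10 and true 2: 6 / (10 × 0.2236) − 1.96 = 0.723, so power is 77%.

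| SD | true 0 | true 1 | true 2 | true 3 |
|---|---|---|---|---|
| 8 | 99% | 97% | 92% | 80% |
| 9 | 98% | 94% | 85% | 70% |
| 10 | 95% | 88% | 77% | 61% |
| 11 | 90% | 81% | 68% | 53% |
| 12 | 85% | 74% | 61% | 46% |

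A t-based check with 78 degrees of freedom, run for true differences of 0 and 2 at SD 8, 10 and 12, lowers these figures by about one percentage point or less (for example 75.5% at SD 10, true 2).

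**Step 3: largest SD that keeps 80% power.** SD = (8 − true) / (2.802 × √(2/40)). This gives 12.8, 11.2, 9.6 and 8.0 at a true disadvantage of 0, 1, 2 and 3 points.

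**Step 4: effect of adjusting for the preoperative score.** With correlation r between the preoperative and 24-month scores, the effective SD is SD × √(1 − r²). The multiplier is 0.954 at r = 0.3 and 0.866 at r = 0.5.

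| SD, true 2 | unadjusted | r = 0.3 | r = 0.5 |
|---|---|---|---|
| 10 | 77% | 80% | 87% |
| 12 | 61% | 65% | 73% |

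At a 2-point disadvantage, the largest SD with 80% power rises from 9.6 to 9.58 / 0.954 = 10.0 at r = 0.3, and to 9.58 / 0.866 = 11.1 at r = 0.5.

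**The case against.** The strongest reply is that the plan already carries a large cushion. On its own inputs 16 per group would meet the only declared margin, yet it plans for 40. With no true difference, the SD could be about 60% larger than 8 (12.8 / 8 = 1.6) before power dropped below 80%. This stands. So does the related point that the cushion covers some joint departures: SD 10 with a 1-point disadvantage keeps 88%, and SD 9 with 2 points keeps 85%.

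A reader might go further and infer that the trial is underpowered and must enrol more patients. The documents do not support that. Nothing in them shows whether the 24-month SD is above or below 8; if it is below, power exceeds the plan's. Rerunning the formula at -5 with a larger SD does not prove a shortfall either, because it keeps the whole cushion while adding a risk that the cushion may be there to cover. Against margin 8 with no true difference, SDs of 10 and 12 need only 25 and 36 per group (2 × 100 × 7.8 / 64 = 24.4; 2 × 144 × 7.8 / 64 = 35.1).

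A reader might also infer from section 3f that a 24-month SD is ready to be looked up. Section 3f describes routine collection in the rhinology practice, while the SD is attributed to otolaryngology practice data. It does not say how many patients return at month 24 or how many had a drill-out.

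Three smaller points also have force. The -5 could be read as an assumed difference, so the accurate criticism is that no true difference is stated separately from the margin. Month-6 and month-12 scores accrue during recruitment and would give some warning about post-operative spread. And section 8b counts the 90 as evaluable; at 45 evaluable per group, SD 10 with a 2-point disadvantage gives 81% rather than 77%.

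These replies do not touch the unused baseline score. Adjusting for it is partly an analyst's choice, but it gains precision whatever the SD turns out to be.

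**Conclusion.** The concern holds in limited form and is minor. The arithmetic in section 3d is right, but its one SD is not matched to the outcome, is not varied, and is not paired with a stated true difference. That is an unsupported input, not a demonstrated shortfall in sample size. The cushion is adequate for moderate departures and inadequate for larger ones, such as SD 10 with a 2-point disadvantage (77%) or SD 12 with 2 points (61%).

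The concrete weakness is the unadjusted interval. Adjusting for the preoperative score would bring the first case to 80-87% and the second to 65-73%, so it helps in both but restores 80% only in the first. These sizes rest on 40 evaluable per group, margin 8, the normal approximation, and assumed SDs, true differences and correlations of 0.3 to 0.5. That the 8.0 is a preoperative figure is an inference from the wording of section 3d, which does not use that term.

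**What to change.** In section 3d:

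1. Prespecify the 95% CI for the 24-month difference in mean SNOT-22 from an ANCOVA with preoperative SNOT-22 as covariate, judged against -8. Make this the analysis unconditionally, not only if the SD proves large.
2. Report power at 40 per group for margin -8 over a stated range of SD and true difference. Use a 24-month SD from practice records if a usable set exists, with the number of patients behind it. If none exists, say so and rely on the range.
3. Label -5 as a planning value only, so that -8 is clearly the decision margin.

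The cost is a few sentences and a small table. There are no new visits, no new data and no change to the planned 90. If the correlation turned out near zero, the adjustment would cost about one degree of freedom. Searching the practice records is some extra work of unknown size, but items 1 and 3 do not depend on it and item 2 can go ahead with an assumed range.
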